#### **Enrollment Exclusion - Randomization**

- Patients who have severe hypercholesterolemia (>350 mg/dL; >9 mmol/L) or hypertriglyceridemia (>500 mg/dL; >8.5 mmol/L) within 6 months of transplantation. Patients with controlled hyperlipidemia are acceptable at the time of randomization.
- Patients with platelet count < 50,000/mm3 at the time of randomization.
- Patients with an absolute neutrophil count of < 1,000/mm^3 or white blood cell count of <2,000/mm^3 at the time of randomization.
- Patients who have tested positive for HIV. Negative laboratory results obtained within 6 months prior to transplant are acceptable.
- Patients with clinically significant systemic infection requiring active use of IV antibiotics at the time of randomization. Patients who are in a critical care setting at the time of randomization requiring life support measures such as mechanical ventilation, dialysis, requirement of vasopressor agents.
- Patients who require renal replacement therapy for clearance within 7 days prior to randomization.
- The presence of thrombosis via Doppler ultrasound of the major hepatic arteries, major hepatic veins, portal vein and inferior vena cava. Results obtained within 5 days prior to randomization are acceptable, however no sooner than Day 25 post-transplantation.
- An episode of acute rejection that required antibody therapy or more than one steroid sensitive episode of acute rejection during the run-in period. This includes patients who have not completed steroid treatment for acute rejection within 7 days prior to randomization.
- Patients with a confirmed spot urine protein-to-creatinine ratio that indicates greater than 0.7 mg protein /mg creatinine. Laboratory results obtained after transplant surgery and within 4 months of randomization are acceptable.
- Use of immunosuppressive agents or treatments after baseline that are not utilized in the protocol.

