### Protocol

Version: December 28, 2018

Randomization will only occur between 90days and 120 days post transplant. Patients randomized between 90 days and 120 days for conversion to Everolimus, in association with Mycophenolic acid, will start Everolimus at a dose of 0.75mg twice daily, with target levels at 3 to 8 ng/mL. Blood levels of Everolimus will be measured by the FDA approved assay by ThermoFisher. The calcineurin inhibitor (tacrolimus or cyclosporine) will be withdrawn after the target levels of Everolimus are reached.Concurrent immunosuppression with MPA will be maintained in both arms with dosage dependant on the degree of bone marrow suppression and leucopenia.

The calcineurin inhibitor (tacrolimus or cyclosporine) will be withdrawn after the target level of Everolimus is reached.

For Tacrolimus: After everolimus blood trough levels have been confirmed to be in the target range (3-8 ng/mL), tacrolimus tapering will begin, targeting a tacrolimus whole blood trough level of 3-5 ng/mL by three weeks after randomization. Once that point is reached tacrolimus elimination will begin while maintaining everolimus whole blood trough levels within the target range of 6-8 ng/mL.

For Cyclosporine: After everolimus blood trough levels have been confirmed to be in the target range (3-8 ng/mL), cyclosporine tapering will begin, targeting a cyclosporine whole blood trough level of 50 to 100 ng/mL by three weeks after randomization. Once that point is reached cyclosporine elimination will begin while maintaining everolimus whole blood trough levels within the target range of 6-8 ng/mL.

Prior to CNI elimination, the inclusion criteria for liver function tests will be re-applied. If a patient does not exhibit a functioning allograft at an acceptable level by as defined by the AST, ALT, Total Bilirubin levels being ≤3 times the upper limits of the normal values (ULN) and Alkaline Phosphatase and Gamma Glutamyl Transferase levels ≤5 times ULN, then the patient will be monitored until these criteria are met, after which tacrolimus/cyclosporine elimination can begin.

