#### Protocol

Version: December 28, 2018

Visit number	1 Screening*	2 Baseline*	3	4	5
Time of Visit	90days-120 days post transplant	90days- 120 days post transplan t	Month 6 +/- 2 weeks***	Month 12 +/- 2 weeks ***	Month 24 +/- 2 weeks ***
Inclusion/Exclusion criteria	Х	Х			
Informed consent	Х				
Physical examination(medical history and vital signs	Х	Х	х	х	Х
Clinical assessment	Х	Х	Х	Х	Х
Quality of Life Questionnaires (FACT-Hep; EQ-5D)	Х	Х	Х	Х	Х
Dispense study medication		Х			
Return study medication					х
Laboratory test (blood & urine collection)	Х	Х	Х	Х	Х
Adverse events		Х	Х	Х	х
Blood test-HIV, hepatitis viruses, CMV and genotyping	Х				
Pregnancy Test	Х				
Concomitant Medications (Standard of Care) **					
Valcyte	Х	Х			
Bactrim(PCP prophylaxis)	Х	Х	Х	Х	
Mycophenolic acid (Myfortic)	Х	Х	Х	Х	Х

\* If the patient meets all inclusion criteria at the Screening Visit, the Screening and Baseline visits may occur on the same day and will occur between 90 days and 120 days post transplant.

\*\*All patients receive CMV prophylaxis with Valcyte in the 1st 4 postoperative months as part of standard care. Bactrim prophylaxis against Pneumocystis carinii is administered for the first year post transplant as part of standard care. Steroids are discontinued at 3 months post-transplant while Myfortic is continued as part of the maintenance immunosuppressive protocol.

\*\*\*Visit window for follow up visits at months 6, 12 and 24 is plus or minus 2 weeks

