#### · Graft Loss/Re-transplant

#### Premature Patient withdrawal:

Patients may voluntarily withdraw from the study or be dropped from it at the discretion of the investigator at any time. Patients will be withdrawn from the study if any of the following occur:

- Withdrawal of consent
- Lost-to follow-up
- Graft loss/re-transplant
- Death
- Serious life threatening adverse event.

If such withdrawal occurs, or if the patient fails to return for visits, the primary reason for a patient's premature withdrawal from the study will be recorded.

For patients who are lost to follow-up, "due diligence" will be shown by documenting in the patient record steps taken to contact the patient, e.g. dates of telephone calls, registered letters, etc.

Patients who are prematurely withdrawn from study medication or from the study after randomization will not be replaced. Patients who withdraw or screen fail prior to randomization will be replaced.

Patients who prematurely discontinue everolimus will be followed for any SAE occurring within 30 days following the last dose of everolimus. These SAEs will be reported on the SAE form.

Patients who become pregnant while taking everolimus or are taking a prohibited immunosuppressive medication not allowed by the protocol will be discontinued from the investigational drug and from the study.

If the everolimus trough level ≥ 3 ng/mL cannot be maintained, patients will be discontinued from the study.

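### An exclusion worded as after baseline largely cannot be checked at randomization, and the matching withdrawal rule ends study follow-up of randomized patients after a post-randomization event

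*Combined protocol and SAP*

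**What the plan says.** All references are to the combined protocol and SAP.

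- **Section 4.0**, under the heading "Enrollment Exclusion - Randomization", ends its list with "Use of immunosuppressive agents or treatments after baseline that are not utilized in the protocol". The same list has a separate exclusion for rejection before entry: "An episode of acute rejection that required antibody therapy or more than one steroid sensitive episode of acute rejection during the run-in period".
- **Section 6.0** sets the timing: "Randomization will only occur between 90days and 120 days post transplant". A footnote to the evaluation schedule says that, for patients who meet the criteria, "the Screening and Baseline visits may occur on the same day and will occur between 90 days and 120 days post transplant". The row "Dispense study medication" is marked only at the Baseline visit. The eligibility row is marked only at Screening and Baseline.
- **Section 10.0**, Premature Patient withdrawal, says that patients who "are taking a prohibited immunosuppressive medication not allowed by the protocol will be discontinued from the investigational drug and from the study". Patients withdrawn after randomization are not replaced. For those who stop everolimus early, the only follow-up specified is for SAEs up to 30 days after the last dose.
- **Section 11.0** compares 24-hour creatinine clearance by t-test, acute rejection by chi-square and time-to-event methods, and patient and graft survival by log-rank test. It names no analysis population and no handling of missing data.

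**The concern.** An eligibility criterion has to be decidable when eligibility is decided. This one points forward from baseline and has no end date. Read with Section 10.0, the effect is that a randomized patient who later receives an immunosuppressant outside the protocol stops contributing study data.

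That event arises after assignment and may be related to outcome. Section 4.0 itself names antibody therapy as a treatment for acute rejection, and antibody therapy belongs to neither arm's regimen in Section 3.0. Rejection at 6, 12 and 24 months is a secondary objective. If such patients leave, the remaining patients are no longer the groups that randomization formed. With 12 per arm, each patient is 1/12 = 8.3% of an arm.

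**Working it through.** **1. Can the bullet be assessed at entry?** Baseline is Visit 2, at day 90 to 120. Randomization has the same window. Study drug is dispensed at Baseline, so assignment is in effect known by then. The order of the two is not stated. If randomization is at or before baseline, none of the period named in the bullet can be assessed. If baseline comes first, only the gap between them can be, and that gap lies inside a 30-day window (120 − 90). The rest of the period runs to month 24.

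**2. What happens after randomization?** Section 10.0 links three things: off drug, off study, not replaced. The month 6, 12 and 24 assessments are study visits, and nothing says that they continue. Routine laboratory tests under Section 7.0 continue to month 24 as standard care and include serum creatinine. The primary endpoint, however, needs the 24-hour urine collection, which is listed among the study tests in Section 6.0.

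**3. Does the analysis section keep these patients?** It is silent on the analysis set. It neither retains nor deletes them, but it leaves no stated route for outcomes that were never collected.

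**4. How much slack is there?** Inputs from Sample size and power in Section 11.0: difference 9.0, SD 7.5, two-sided alpha 0.05, 12 per group, 80% power; also 51 per group at SD 16.

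Formula: power = P(|T| > t critical), where T is noncentral t with df = n1 + n2 − 2 and noncentrality δ = difference / [SD × √(1/n1 + 1/n2)].

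Reproducing the plan first: for 12 v 12, δ = 9 / (7.5 × √(1/12 + 1/12)) = 9 / 3.062 = 2.94 with df 22, giving power 0.802. With 11 per group power is 0.763, so 12 is the minimum. At SD 16, 51 per group gives 0.803. Both stated figures reproduce.

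Then with assumed losses from one arm:

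| Patients left | df | δ at SD 7.5 | Power, SD 7.5 | Power, SD 16 |
|---|---|---|---|---|
| 12 v 12 | 22 | 2.94 | 0.802 | 0.261 |
| 11 v 12 | 21 | 2.87 | 0.783 | 0.251 |
| 10 v 12 | 20 | 2.80 | 0.760 | 0.240 |
| 9 v 12 | 19 | 2.72 | 0.733 | 0.228 |

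**5. How would bias scale?** If k of 12 patients in an arm are lost and their mean clearance differs by d from those kept, the mean of those kept differs from the full-arm mean by (k/12) × d. For k from 1 to 3 and d from 5 to 15 mL/min, both assumed, the shift runs from 1/12 × 5 = 0.42 to 3/12 × 15 = 3.75 mL/min. In size that is 5% to 42% of the planning difference of 9. The documents give neither k nor d, nor the sign of d, so this shows scale only. The 9 is stated for eGFR and serves here only as a yardstick for creatinine clearance.

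**The case against.** The best defence is that the bullet never operates during follow-up. It sits in an entry list, and the schedule marks eligibility only at Screening and Baseline. Screening and Baseline may share a day but need not, so a short interval before randomization is possible. This stands: a reader might infer that the bullet itself drops randomized patients, but the documents do not say that it is re-applied. The removal rule is the one in Section 10.0, and rewording the bullet alone would leave that rule in force.

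Three further inferences are tempting and not supported.

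- **That the trigger is rejection.** The bullet gives no reason for use, and no list says which agents fall outside the protocol. Corticosteroids, calcineurin inhibitors and mycophenolic acid are all protocol drugs, so a steroid-treated episode or a return to a calcineurin inhibitor may not count. Antibody therapy is the clear example.
- **That loss is uneven by arm.** The bullet is neutral between arms. The Section 10.0 wording refers to the investigational drug, which only Arm A receives, so its application to Arm B is unclear. That does not establish a difference in loss.
- **That recorded rejection episodes disappear and the rejection rate falls.** Rejection would precede its treatment, and no text deletes an event already recorded or says that these patients leave the analysis. What is lost is what happens afterwards.

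It can also be said that the power figures would apply to any withdrawal, and that other removal rules in Sections 7.0 and 10.0 raise the same issue. Both are true. Neither removes the contradiction in timing or the loss of follow-up under this rule.

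**Conclusion.** The point holds as a defect of design and wording that should be corrected. The eligibility bullet refers largely or wholly to time that cannot be assessed at randomization. Section 10.0, followed as written, ends study data collection for randomized patients because of a post-randomization event that may be related to outcome, and Section 11.0 has no analysis population to protect the comparison.

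The size is not known. The documents give no rate of non-protocol immunosuppression, and neither the direction nor the amount of bias in the renal, rejection or survival comparisons can be derived from them. What can be shown is the thin margin: on the plan's own SD of 7.5 and difference of 9, each of the first three patients lost from one arm costs about 2 to 3 percentage points of power, from 0.802 down to 0.733. This rests on assumed losses. The stated sample size is correct on its own inputs.

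**What to change.** 1. **Section 4.0 and the evaluation schedule.** State the order of baseline and randomization, and limit the bullet to a period that can be assessed at randomization.
2. **Section 10.0.** Separate stopping study drug from leaving the study, and say how the rule applies to Arm B. Whether and when study drug stops is for the sponsor to decide and is not part of this point.
3. **Sections 10.0 and 11.0.** State that patients who receive non-protocol immunosuppression after randomization continue the month 6, 12 and 24 assessments unless they withdraw consent, that the use is recorded, and that they are analysed in their assigned arm.

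The first two changes must be made together; otherwise the new follow-up statement would contradict Section 10.0. The cost is an amendment to a few sentences and continued scheduled study tests, chiefly renal, for a few patients. The estimate will then include outcomes after off-protocol therapy, which the report should say. If all 12 per arm are followed and analysed, the planned power of 0.802 stands on the plan's assumptions.

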# 5.0 Recruitment and Consent Process

The primary investigator, [name], will obtain consent and discuss in detail the process of randomization and the risks and benefits of the study both at time of admission for transplant and between 90 days-120 days post-operatively. Patients will be provided with a copy of the consent form at time of transplant to allow them to consider participation in the study between 90 day-120 day time point. Patients will also be seen regularly on an outpatient basis for routine follow up in the first 3 months of transplant, at which point any additional questions they may have about the study can be addressed. Between 90 days-120 days post transplant, patients will be seen on an outpatient basis and will be asked if they are interested in participation, during which time the study randomization process and consent process will again be undertaken in detail.

# 6.0 Study Procedures

Conversion from CNI to Everolimus in Arm A:

Amendment 6Page 6 of 18

IRB # 38115

### Protocol

Version: December 28, 2018

Randomization will only occur between 90days and 120 days post transplant. Patients randomized between 90 days and 120 days for conversion to Everolimus, in association with Mycophenolic acid, will start Everolimus at a dose of 0.75mg twice daily, with target levels at 3 to 8 ng/mL. Blood levels of Everolimus will be measured by the FDA approved assay by ThermoFisher. The calcineurin inhibitor (tacrolimus or cyclosporine) will be withdrawn after the target levels of Everolimus are reached.Concurrent immunosuppression with MPA will be maintained in both arms with dosage dependant on the degree of bone marrow suppression and leucopenia.

The calcineurin inhibitor (tacrolimus or cyclosporine) will be withdrawn after the target level of Everolimus is reached.

For Tacrolimus: After everolimus blood trough levels have been confirmed to be in the target range (3-8 ng/mL), tacrolimus tapering will begin, targeting a tacrolimus whole blood trough level of 3-5 ng/mL by three weeks after randomization. Once that point is reached tacrolimus elimination will begin while maintaining everolimus whole blood trough levels within the target range of 6-8 ng/mL.

For Cyclosporine: After everolimus blood trough levels have been confirmed to be in the target range (3-8 ng/mL), cyclosporine tapering will begin, targeting a cyclosporine whole blood trough level of 50 to 100 ng/mL by three weeks after randomization. Once that point is reached cyclosporine elimination will begin while maintaining everolimus whole blood trough levels within the target range of 6-8 ng/mL.

Prior to CNI elimination, the inclusion criteria for liver function tests will be re-applied. If a patient does not exhibit a functioning allograft at an acceptable level by as defined by the AST, ALT, Total Bilirubin levels being ≤3 times the upper limits of the normal values (ULN) and Alkaline Phosphatase and Gamma Glutamyl Transferase levels ≤5 times ULN, then the patient will be monitored until these criteria are met, after which tacrolimus/cyclosporine elimination can begin.

Everolimus and CNI trough concentrations will be measured twice a week for the first 6 months after transplant. After 6 months, trough concentrations may be measured on a weekly basis until end of month 12 post transplant, after which levels maybe measured on a q2weekly basis. Patients seen in the post liver transplant clinic may have an additional measurement performed that day in conjunction with their routine laboratory work.

#### Target levels for Arm B:

The most common CNI used at our institution is prograf (Tacrolimus) & at 3 months the level is maintained at 10-12 ng/mL unless the patient has hepatitis C where the levels are kept at a slightly lower level of 8-10 ng/mL. Concurrent immunosuppression with MPA will be maintained in arm B with dosage dependant on the degree of bone marrow suppression and leucopenia. If cyclosporine is utilized, the level at 3 months is maintained at the 200 to 250 ng/mL range unless the patient has hepatitis C where the levels are kept at a slightly lower level of 150 to 200 ng/mL.

#### Study duration:

Start Date: 1 October 2012

End Date: 1 October 2019

2 year subject enrollment..

#### Evaluation schedule:

Amendment 6Page 7 of 18

PRAMS00038115 Approval: 1/7/2020

IRB # 38115

#### Protocol

Version: December 28, 2018

Visit number	1 Screening*	2 Baseline*	3	4	5
Time of Visit	90days-120 days post transplant	90days- 120 days post transplan t	Month 6 +/- 2 weeks***	Month 12 +/- 2 weeks ***	Month 24 +/- 2 weeks ***
Inclusion/Exclusion criteria	Х	Х			
Informed consent	Х				
Physical examination(medical history and vital signs	Х	Х	х	х	Х
Clinical assessment	Х	Х	Х	Х	Х
Quality of Life Questionnaires (FACT-Hep; EQ-5D)	Х	Х	Х	Х	Х
Dispense study medication		Х			
Return study medication					х
Laboratory test (blood & urine collection)	Х	Х	Х	Х	Х
Adverse events		Х	Х	Х	х
Blood test-HIV, hepatitis viruses, CMV and genotyping	Х				
Pregnancy Test	Х				
Concomitant Medications (Standard of Care) **					
Valcyte	Х	Х			
Bactrim(PCP prophylaxis)	Х	Х	Х	Х	
Mycophenolic acid (Myfortic)	Х	Х	Х	Х	Х

\* If the patient meets all inclusion criteria at the Screening Visit, the Screening and Baseline visits may occur on the same day and will occur between 90 days and 120 days post transplant.

\*\*All patients receive CMV prophylaxis with Valcyte in the 1st 4 postoperative months as part of standard care. Bactrim prophylaxis against Pneumocystis carinii is administered for the first year post transplant as part of standard care. Steroids are discontinued at 3 months post-transplant while Myfortic is continued as part of the maintenance immunosuppressive protocol.

\*\*\*Visit window for follow up visits at months 6, 12 and 24 is plus or minus 2 weeks

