# 4.0 Inclusion and Exclusion Criteria

Study Population: This will be a pilot study which will include 12 adult deceased donor liver transplant recipients in each study arm.

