### Exclusion

- Patients who are recipients of multiple solid organ or islet cell tissue transplants, or have previously received an organ or tissue transplant. Patients who have a combined liver kidney transplant.
- Recipients of a liver from a living donor, or of a split liver.
- History of malignancy of any organ system within the past 5 years whether or not there is evidence of local recurrence or metastases, other than non-metastatic basal or squamous cell carcinoma of the skin or HCC (see next criteria).
- Hepatocellular carcinoma that does not fulfill Milan criteria (1 nodule ≤ 5 cm, 2-3 nodules all < 3 cm, seen at the time of transplantation as per explant histology of the recipient liver.
- Any use of antibody induction therapy.
- Patients with a known hypersensitivity to the drugs used on study or their class, or to any of the excipients.
- Patients who are recipients of ABO incompatible transplant grafts.
- Recipients of organs from donors who test positive for Hepatitis B surface antigen or HIV are excluded.
- Patients who have any surgical or medical condition, which in the opinion of the investigator, might significantly alter the absorption, distribution, metabolism and excretion of study drug.
- Women of child-bearing potential (WOCBP), defined as all women physiologically capable of becoming pregnant, including women whose career, lifestyle, or sexual orientation precludes intercourse with a male partner and women whose partners have been sterilized by vasectomy or other means, UNLESS (1) they meet the following definition of post-menopausal: 12 months of natural (spontaneous) amenorrhea or 6 months of spontaneous amenorrhea with serum FSH levels >40 mIU/m, or (2) have past 6 weeks from surgical bilateral oophorectomy with or without hysterectomy or (3) are using one or more of the following acceptable methods of contraception: surgical sterilization (e.g., bilateral tubal ligation, vasectomy), hormonal contraception (implantable, patch, oral), copper coated IUD and double-barrier methods ( any double combination of male or female condom with spermicidal gel, diaphragm, sponge, cervical cap). Periodic abstinence (e.g., calendar, ovulation, symptothermal, post-ovulation methods) and withdrawal are not acceptable methods of contraception. Reliable contraception should be maintained throughout and for 3 months after study drug discontinuation.

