#### Side effects of lothalamate clearance test:

Rare allergic reactions to iothalamate in subjects known to be allergic to iodine. Can range from urticaria to anaphylactic shock. Other adverse effects of iothalamate include arrythmias, bradycardia, generalized vasodilation, extravasation of iothalamate during injection, seizures, and weakness of extremities. Abnormal sensation or muscle spasm in the injection site has been reported but in patients being infused with five to thirteen times the amount planned in this study and at a faster infusion rate.

Mycophenolic acid has bone marrow suppression as the main side effect and rarely may have neurotoxicity associated with it. It is also an enteric coated formulation and hence should have less of the GI side effects such as nausea, vomiting and diarrhea, than mycophenolic mofetil which is a similar drug.

Given that arm A will consist of the patients on everolimus and mycophenolic acid, with complete withdrawal of calcineurin inhibitor, there will be a risk of bone marrow suppression and leucopenia, which will be dosage dependent.

Both calcineurin inhibitors and mycophenolic acid increase the patient risk for cancer, especially post transplant lymphoproliferative disease. Everolimus is thought to have an antiproliferative effect and may reduce the risk for the development of cancer.

All patients will be monitored closely for any of the above side effects. Other than the scheduled study clinic visits and testing, allpatients will be followed as per the Penn State Division of Transplantation follow up guidelines. For the first 24 months post liver transplant all our patients undergo the following routine lab collection procedure, the frequency of which may be adjusted based on patient clinical status and need:

Routine/standard of care laboratory tests from post op month 1 through post op month 24 include: :

✓ 1st 5 months postop: 2x/week labs as follows: Sodium, Potassium, Chloride, Bicarbonate level, BUN, Creatinine, Magnesium, Calcium, Phosphorus, CBC, PT, INR, PTT, Liver Function Tests (Total & Direct Bilirubin, AST, ALT, Alkaline Phosphatase & Gamma Glutamyl Transferase), Glucose & Immunosuppressive agent trough levels. Lipid Panel to be performed once a week.

PRAMS00038115 Approval: 1/7/2020

IRB # 38115

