# 14.0 Compensation

For patients randomized into Group A who are receiving Everolimus medication will be reimbursed for travel expenses in order to return twice per week during the first 3 months after randomization to have the Everolimus blood level checked at Hershey Medical Center's Laboratory. The reimbursement for travel expense is 24 cents per mile based on the 2013 Internal Revenue Service standard mileage reimbursement rate for medical travel and the total repayment will not exceed \$300.00. If the patient does not complete the study for any reason during the first 3 months after randomization, the patient will be paid for the medical travel expense up to the time of study discontinuation.

For patients randomized into Group B who are receiving Tacrolimus or Cyclosporin and Mycophenolic acid medications will not receive any payment or compensation for being in this research study because they may continue to have medication blood levels checked at the local laboratory with blood level results faxed to [name] office

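### The schedule marks a pregnancy test at Screening only, so a woman of child-bearing potential has no scheduled test while on everolimus, although pregnancy requires stopping drug and study: a minor, cheap safety improvement.

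*Combined protocol and SAP*

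**What the plan says.** The section 6.0 evaluation schedule has a separate row "Pregnancy Test", marked in the Screening column and blank at Baseline and at Months 6, 12 and 24. In the same table the row beginning "Laboratory test (blood & urine collection" is marked at all five visits. The list of tests under that schedule names renal function measures, genotyping and testosterone. The routine panels in section 7.0 name chemistry, blood count, coagulation, liver tests, glucose, drug troughs and lipids. Neither list includes a pregnancy test.

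The exclusion criteria in section 4.0 let a woman of child-bearing potential enter if, among other routes, she is one of those who "are using one or more of the following acceptable methods of contraception". Surgical sterilization is among the methods listed. Contraception must continue through the study and for three months after the drug is stopped.

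Section 10.0, on premature withdrawal, covers "Patients who become pregnant while taking everolimus" and requires that they come off the drug and leave the study. Section 4.0 plans "12 adult deceased donor liver transplant recipients in each study arm".

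**The concern.** The plan treats pregnancy on everolimus as something to prevent and as a reason to stop. A stopping rule can act only once the event is known. The rules for low blood counts, lipids and everolimus trough are backed by repeated scheduled laboratory tests; the pregnancy rule has none after Screening. An early pregnancy that history and examination did not reveal could remain exposed to the drug until something else brought it to light.

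A smaller point concerns the start of treatment. Screening and Baseline may be on one day, but need not be. If they are apart, the drug is dispensed at Baseline on the strength of a test done earlier.

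Participant safety in a small subgroup is what is at stake. Renal function, the treatment comparison and the power calculation are untouched.

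**Working it through.** The plan states no figure for the untested interval, so there is none to reproduce. The check is a count of marks and date arithmetic.

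**Inputs**
- Randomization, and so the everolimus start: day 90 to 120 after transplant (section 6.0).
- Final study visit: 24 months after transplant (section 7.0). With a month of 365/12 days, Month 24 = day 730, Month 12 = day 365 and Month 6 = day 183.
- Visit window at Months 6, 12 and 24: plus or minus 14 days (section 6.0 schedule).
- Planned Arm A size: 12 (section 4.0).

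**Scheduled tests after Screening**

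Marks at Baseline, Month 6, Month 12 and Month 24: 0 of 4.

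**Interval without a scheduled test, if everolimus is taken to Month 24**
- Shortest: 730 − 120 = 610 days.
- Longest: 730 − 90 = 640 days.
- With the window: 610 − 14 = 596 to 640 + 14 = 654 days.

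**Age of the Screening test at dispensing**

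0 days if both visits are on one day; at most 120 − 90 = 30 days otherwise.

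**Intervals if the row is also marked at Months 6, 12 and 24**

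| Interval | Nominal days | With window |
|---|---|---|
| Baseline to Month 6 | 183 − 120 = 63 to 183 − 90 = 93 | 49 to 107 |
| Month 6 to Month 12 | 365 − 183 = 182 | 154 to 210 |
| Month 12 to Month 24 | 730 − 365 = 365 | 337 to 393 |

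The longest interval falls from 610–640 days to about 365 days. About a year remains between the last two tests, which is why a test at an intervening clinic visit is worth allowing.

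**Number of tests**

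Three per affected woman, or four with a separate Baseline. The ceiling, if every Arm A patient were such a woman, is 12 × 4 = 48. The documents do not give the expected number.

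**The case against.** The strongest reply is that existing controls already run at a close interval. Section 4.0 requires contraception and rejects periodic abstinence and withdrawal. Section 7.0 has clinic visits at 6 and 9 months, section 6.0 has a Month 12 visit, and in Years 2 and 3 clinic is every three months, with history and examination at clinic visits. A woman is thus seen about every 91 days, and nothing bars a test on suspicion. This stands. It leaves as the real increment an early pregnancy, in a woman using required contraception, that history and examination miss. It does not supply a scheduled test.

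A reader might draw stronger conclusions, and the documents do not support them:

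- **That a pregnancy could go unnoticed for 20 to 21 months.** The 610 to 640 days is the distance between calendar points. It assumes everolimus to Month 24, although sections 7.0 and 10.0 give several routes to earlier discontinuation, and it ignores the clinic contacts above.
- **That the plan contradicts itself.** Section 10.0 says what follows if pregnancy occurs; it does not promise scheduled testing.
- **That a quarterly test calendar is needed.** Nothing in the documents sets such an interval. Nor are the trough draws a firm frame for one. After month 12 the text reads "after which levels maybe measured on a q2weekly basis", and for routine laboratory work it adds "the frequency of which may be adjusted based on patient clinical status and need". Section 14.0 funds travel for Arm A patients to "return twice per week during the first 3 months after randomization" and does not say where later draws are taken.
- **That the harm is large.** The everolimus risks listed in section 7.0 do not include an embryo-fetal risk, and no document quantifies one. The contraception and withdrawal rules show caution and no more. What patients were told at consent cannot be judged, because those pages are not available.

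**Conclusion.** The gap is real: no pregnancy test is scheduled after Screening for a woman of child-bearing potential on everolimus, for up to 610 to 640 days nominally, while pregnancy obliges her to stop drug and study. Contraception and roughly three-monthly history and examination reduce the risk but do not test for it. Few women are likely to be affected, somewhere between 0 and 12.

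This is a minor patient-safety improvement, worth making because it is cheap. The size rests on three assumptions: months are counted from transplant, everolimus is continued to Month 24, and only scheduled tests count. Tests done on suspicion are outside the claim.

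**What to change.** For women of child-bearing potential who are receiving everolimus and are not surgically sterilized:

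1. Mark the pregnancy-test row at Months 6, 12 and 24, using the blood or urine already collected at those visits. Month 24 matters because study medication is returned then, and the test closes the last interval.
2. If Baseline is not on the same day as Screening, repeat the test at Baseline before dispensing.
3. Allow, as an option, extra tests at routine clinic visits between Months 12 and 24, where the longest interval remains.

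The cost is three low-cost tests per affected woman, four with a separate Baseline, and no new visit. The schedule row and a footnote need a minor amendment with ethics board approval, and the team must identify the eligible women and follow up results.
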